5. SUBJECT ENROLLMENT

Before subjects begin participation in any study-specific activities/procedures, Amgen requires a copy of the site's written institutional review board/independent ethics committee (IRB/IEC) approval of the protocol, informed consent form (ICF) (see [Section 11.2](#)). All subjects or legally acceptable representatives must personally sign and date the ICF before commencement of study-specific activities/procedures.

Subject is considered enrolled when **the investigator decides that the subject has met all eligibility criteria. The investigator decision and date of enrollment must be documented in the subject's medical records.**

The Investigator is to document the enrollment decision and date, in the subject's medical record and in/on the enrollment case report form (CRF).

Each subject who enters into the screening period for the study receives a unique subject identification number before any study procedures are performed.

For phase 1, the subject identification number will be assigned manually and for phase 2, the subject identification number will be assigned by Interactive Voice Response System (IVRS)/Interactive Web Response System (IWRS). The subject identification number must remain constant throughout the entire clinical study; it must not be changed after initial assignment, including if a subject is rescreened.

Approved

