9. SAFETY DATA COLLECTION, RECORDING, AND REPORTING

9.1 Definition of Safety Events

9.1.1 Adverse Events

An adverse event is defined as any untoward medical occurrence in a clinical trial subject. The event does not necessarily have a causal relationship with study treatment. The investigator is responsible for ensuring that any adverse events observed by the investigator or reported by the subject are recorded in the subject's medical record.

The definition of adverse events includes worsening of a pre-existing medical condition.

Worsening indicates that the pre-existing medical condition or underlying disease (eg, diabetes, migraine headaches, gout) has increased in severity, frequency, and/or duration more than would be expected and/or has an association with a significantly worse outcome than expected. A pre-existing condition that has not worsened more than anticipated (ie, more than usual fluctuation of disease) during the study, or involves an intervention such as elective cosmetic surgery or a medical procedure while on study, is not considered an adverse event.

If the severity of an adverse event changes from the date of onset to the date of resolution, record as a single event with the highest grade on the Events eCRF.

For situations when an adverse event or serious adverse event is due to non-small cell carcinoma of lung, colorectal cancer, or pancreatic adenocarcinoma report all known signs and symptoms. Death due to disease progression in the absence of signs and symptoms should be reported as the primary tumor type (eg, metastatic pancreatic cancer).

Note: The term “disease progression” should not be used to describe the adverse event.

The investigator’s clinical judgment is used to determine whether a subject is to be removed from treatment due to an adverse event. In the event a subject, or subject’s legally acceptable representative requests to withdraw from protocol-required therapies or the study due to an adverse event, refer to [Section 8.1](#) for additional instructions on the procedures recommended for safe withdrawal from protocol-required therapies or the study.

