9.2 Safety Event Reporting Procedures

9.2.1 Adverse Events

9.2.1.1 Reporting Procedures for Adverse Events That do not Meet Serious Criteria

The investigator is responsible for ensuring that all adverse events observed by the investigator or reported by the subject that occur after enrollment through the safety follow-up visit are reported using the Event CRF.

The investigator must assign the following adverse event attributes:

- Adverse event diagnosis or syndrome(s), if known (if not known, signs or symptoms),
- Dates of onset and resolution (if resolved),
- Severity and/or toxicity per protocol,
- Assessment of relatedness to investigational product and
- Action taken.

The adverse event grading scale used will be the CTCAE version 5.0. The grading scale used in this study is described in [Appendix A](#). The investigator must assess whether the adverse event is possibly related to AMG 510 [REDACTED]. For each agent this relationship is indicated by a “yes” or “no” response to the questions: ‘Is there a reasonable possibility that the event may have been caused by **investigational product?**’ and [REDACTED].

The investigator must assess whether the adverse event is possibly related to any study mandated activity (eg, administration of investigational product, protocol-required therapies, use of medical device(s) and/or procedure (including any screening procedure(s))). This relationship is indicated by a “yes” or “no” response to the question: “Is there a reasonable possibility that the event may have been caused by a study activity (eg, administration of investigational product, protocol-required therapies, use of medical device(s)), and/or procedure”?

The investigator is responsible for reviewing laboratory test results and determining whether an abnormal value in an individual study subject represents a clinically significant change from the subject’s baseline values. In general, abnormal laboratory findings without clinical significance (based on the Investigator's judgment) are not to be recorded as adverse events. However, laboratory value changes that require treatment or adjustment in current therapy are considered adverse events. Where applicable,

clinical sequelae (not the laboratory abnormality) are to be recorded as the adverse event.

The investigator is expected to follow reported adverse events until stabilization or reversibility.

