9.2.1.2 Reporting Procedures for Serious Adverse Events

The investigator is responsible for ensuring that all serious adverse events observed by the investigator or reported by the subject that occur after signing of the informed consent through 30 days after the last day of the dosing interval of investigational product are recorded in the subject's medical record and are submitted to Amgen. Serious adverse events observed by the investigator or reported by the subject that occur after the safety follow-up visit through the end of the long-term follow-up period should be reported if there is a reasonable possibility that the event may have been caused by AMG 510. All serious adverse events must be submitted to Amgen within 24 hours following the investigator's knowledge of the event via the Event CRF.

If the electronic data capture (EDC) system is unavailable to the site staff to report the serious adverse event, the information is to be reported to Amgen via an electronic Serious Adverse Event (eSAE) Contingency Report Form within 24 hours of the investigator's knowledge of the event. See [Appendix B](#) for a sample of the Serious Adverse Event Worksheet/electronic Serious Adverse Event Contingency Report Form.

The investigator must assess whether the serious adverse event is possibly related to the investigational product. This relationship is indicated by a "yes" or "no" response to the question: Is there a reasonable possibility that the event may have been caused by the investigational product(s), and/or other protocol-required therapies? Relatedness means that there are facts or reasons to support a relationship between investigational product and the event.

The investigator is expected to follow reported serious adverse events until stabilization or reversibility.

New information relating to a previously reported serious adverse event must be submitted to Amgen. All new information for serious adverse events must be sent to Amgen within 24 hours following knowledge of the new information. If specifically requested, the investigator may need to provide additional follow-up information, such as discharge summaries, medical records, or extracts from the medical records.

Information provided about the serious adverse event must be consistent with that recorded on the Event CRF.

If a subject is permanently withdrawn from protocol-required therapies because of a serious adverse event, this information must be submitted to Amgen.

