It is defined as the first day of the treatment being administered to the subject.

Time to Response (TTR):

Time to response is defined as time from the start of treatment until the first evidence of confirmed PR or CR. TTR will be calculated only for subjects who achieve a best overall response of PR or better

Treatment-Emergent Adverse Event (TEAE):

Events categorized as Adverse Events (AEs) starting on or after first dose of investigational product as determined by the flag indicating if the adverse event started prior to the first dose on the Events CRF and up to and including 30 days after the last dose of investigational product or the End of Study date, whichever is earlier.

Treatment-Related AE:

A treatment-related AE is any treatment-emergent AE that per investigator review has a reasonable possibility of being caused by the investigational product.

Toxicity Probability Interval (TPI):

Toxicity probability intervals for dose-limiting toxicity (DLT) are defined as (0.20, 0.33] and (0.33, 1.00] for target and excessive, respectively.

6. Analysis Sets

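### An adverse event that starts before first dose and worsens on AMG 510 falls outside the treatment-emergent and treatment-related definitions

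*Supplement*

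**What the plan says.** The latest documents are Protocol Amendment 3 and SAP Amendment 1 (v2.0).

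- **Enrollment.** Under Protocol section 5 a subject is enrolled when "the investigator decides that the subject has met all eligibility criteria". Section 5.1 requires confirmation of enrollment before the day 1 dose.
- **Collection.** Protocol 9.2.1.1 covers non-serious events "that occur after enrollment through the safety follow-up visit are reported using the Event CRF". Protocol 9.2.1.2 covers serious events "that occur after signing of the informed consent through 30 days after the last day of the dosing interval", also on the Event CRF.
- **Severity changes.** When severity changes between onset and resolution, Protocol 9.1.1 tells the site to "record as a single event with the highest grade on the Events eCRF".
- **Treatment emergence.** SAP section 5 counts "Events categorized as Adverse Events (AEs) starting on or after first dose of investigational product as determined by the flag"; that flag, on the Events CRF, marks an event that began before the first dose. The window closes 30 days after the last dose or at End of Study, whichever is earlier.
- **Treatment-related.** SAP section 5: "A treatment-related AE is any treatment-emergent AE that per investigator review has a reasonable possibility of being caused by the investigational product".

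**The concern.** A treatment-emergent definition should catch toxicity that appears or gets worse once the drug is given. This one looks only at when the event started. Because collection opens before dosing and a worsening event keeps its original record, some on-drug worsening carries a pre-dose start. The relatedness definition is nested inside treatment emergence, so an investigator's judgment that the worsening was caused by AMG 510 does not bring the event back.

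Incidence of treatment-emergent and treatment-related events is part of the phase 1 primary safety endpoint (Protocol 10.1.1.1.1.1; SAP 2.1.1). In those tables the rule can only under-count, and what it omits is toxicity that increased on treatment.

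**Working it through.** No arithmetic applies; the question is how the rules combine. One case, followed through the two documents:

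| Step | Rule | Result |
|---|---|---|
| Subject is judged eligible; dosing has not begun | Protocol 5 and 5.1 | Enrolled, pre-dose |
| A grade 1 event starts | Protocol 9.2.1.1 (from consent if serious, 9.2.1.2) | Event CRF record opened with a pre-dose start |
| First dose is given with the event unresolved | – | Record stays open |
| The event reaches grade 3 on drug | Protocol 9.1.1 | Same record, highest grade 3, no new start date |
| Flag for start before first dose | SAP 5 | Pre-dose start |
| Treatment-emergent? | SAP 5 | No |
| Treatment-related? | SAP 5 | No, whatever the investigator's causality answer |
| Tables of treatment-emergent events by term and by grade | SAP 9.6.2 | Absent |

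Three checks on this trace:

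1. **Start-date convention.** The sample serious adverse event form (Protocol Appendix B) asks for the date the event first began rather than the date it became serious. It has a separate box for events before first dose. That agrees with the trace.
2. **Any rule that reclassifies the event.** The SAP's treatment-emergent definition has no worsening clause, and nothing else shown in either document moves such a record into the treatment-emergent set.
3. **Other outputs that could show the event.** SAP 9.6.2 also tabulates serious events, fatal events and events leading to withdrawal, and does not clearly limit these to treatment-emergent events. SAP 9.6.3 tabulates laboratory shifts from baseline to the worst on-study value, so graded laboratory worsening appears there whatever the flag says. The table by relationship in SAP 9.6.2 speaks of adverse events generally and could literally include the record, but the section 5 definition of a treatment-related event points the other way.

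**The case against.** The strongest reply is that both documents already treat worsening of a pre-existing condition as an adverse event (Protocol 9.1.1; SAP 5). Such worsening after dosing gets its own post-dose start and counts as treatment-emergent. This stands for medical history and removes most baseline conditions from the problem. It does not clearly reach an event already on the Event CRF, because the single-record instruction in the same section speaks directly to a change of severity in a reported event. At the least, section 9.1.1 does not say which instruction governs, and sites could code such cases differently.

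A second reply is that the toxicity is not lost from the report. That is largely right for serious, fatal and withdrawal events and for graded laboratory worsening, as shown above. Dose-level review also considers events in all subjects (Protocol 10.4.1.1; SAP 7.1.1). None of this corrects the treatment-emergent and treatment-related tables.

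A third is that the Events CRF and its completion instructions are not in the supplement and might already call for a new record. That cannot be excluded, but it would contradict Protocol 9.1.1 as written.

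Some stronger readings are tempting and not supported:

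- **Phase 2 endpoint.** A reader might infer that the phase 2 safety endpoint is mis-measured in the same way. That endpoint is incidence and severity of adverse events with no treatment-emergent qualifier (Protocol 10.1.1.2.2); in phase 2 only the treatment-emergent tables are affected.
- **A 7-day exposure window.** Protocol 7.2 allows the start of treatment to be delayed by up to 7 days, but does not count that delay from enrollment.
- **DLT counts.** The SAP's DLT definition refers to onset after first dose. It also points to the criteria in Protocol 6.1.1.2.1, which speak of events occurring during cycle 1, so the documents do not settle whether such an event would be missed there.

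**Conclusion.** The gap is real and follows from the stated rules. It is confined to an event that starts after enrollment (or a serious event after consent) and before first dose, is still unresolved at first dose, and then worsens on AMG 510. Such an event is excluded from the treatment-emergent and treatment-related tables behind the phase 1 primary safety endpoint and from the treatment-emergent tables by grade in both phases.

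Its size cannot be estimated from the documents, which state neither a pre-dose event rate nor the interval from enrollment to dosing. A reader might want a count. With purely assumed rates, 3% to 8% of 158 + 200 = 358 planned subjects having a pre-dose event and 10% to 30% of those events worsening, the arithmetic gives 358 × 0.03 × 0.10 = 1.1 to 358 × 0.08 × 0.30 = 8.6 subjects. That range only restates the assumptions and should not be quoted as an expected loss. The interval is probably short and the effect probably small. The case for changing the text rests on the direction of the error, the role of these tables in phase 1 and the low cost. The conclusion assumes that sites follow the single-record instruction as written.

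**What to change.** Both parts are needed, because a single highest-grade record holds no date of worsening and a new SAP definition could not be applied to it alone.

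1. **SAP section 5.** Define a treatment-emergent event as *an adverse event that starts, or increases in CTCAE grade, on or after first dose and within the window*. The treatment-related definition then follows without change.
2. **Protocol 9.1.1 and the CRF completion instructions.** State that when an event with onset before first dose worsens after first dose, the worsening is recorded as a new event with its own start date, grade and relatedness. The single-record rule can stay for events that start on treatment.

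The cost is a small amendment to Protocol 9.1.1, a CRF instruction and one SAP sentence.

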7.2.3 End-of-treatment Visit

For subjects who discontinue investigational product, the EOT visit should occur as soon as possible (within 14 days) after the last dose of investigational product.

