Appendix B. Sample Serious Adverse Event Form

Completion Instructions - Electronic Adverse Event Contingency Report Form (For use for clinical trial studies using Electronic Data Capture [EDC])

NOTE: This form is to be used under restricted conditions outlined on page 1 below. If you must fax an event report to Amgen, you must also enter that event into the EDC system (eg, Rave) when it becomes available.

General Instructions

The protocol will provide instruction on what types of events to report for the study. This form is to be used ONLY to report events that must be captured in the Amgen safety database. *Indicates a mandatory field.

Types of Events to be reported on this form

- Serious Adverse Events (regardless of causal relationship to IP)

1. Site Information

Site Number* – Enter your assigned site number for this study

Investigator*, Country*, Reporter*, Phone No., and Fax No. – Enter information requested

2. Subject Information

Subject ID Number* – Enter the entire number assigned to the subject

Age at event onset, Sex, and Race – Enter the subject's demographic information

End of Study date – If the subject has already completed the study or terminated the study early, enter the End of Study date

If you are submitting follow-up information to a previous report, provide the serious adverse event term for the previous report as well as the start date for the initial event.

3. Serious Adverse Event

Provide the date the Investigator became aware of this Information

Serious Adverse Event Diagnosis or Syndrome* –

➤ If the diagnosis is known, it should be entered. Do not list all signs/symptoms if they are included in the diagnosis.

➤ If a diagnosis is not known, the relevant signs/symptoms should be entered.

➤ If the event is fatal, the cause of death should be entered and autopsy results should be submitted, when available.

Date Started* – Enter date the adverse event first started (not the date on which the event met serious criteria) rather than the date of diagnosis or hospitalization. This is a mandatory field.

Date Ended – Enter date the adverse event ended and not the date when the event no longer met serious criteria. If the event has not ended at the time of the initial report, a follow-up report should be completed when the end date is known. If the event is fatal, enter the date of death as the end date.

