The duration of complete response is defined as time from the first evidence of CR to disease progression or death due to any cause.

DOR will be calculated only for subjects who achieve a confirmed best overall response of PR or better.

Subjects will be censored following the censoring strategy described in the definition of PFS time in [Table 1](#).

Duration of stable disease:

Duration of stable disease will be measured from the start of treatment to disease progression or death due to any cause.

Subjects will be censored following the censoring strategy described in the definition of the PFS time in [Table 1](#).

End of IP administration (End of IP Admin):

End of IP Admin for each subject is defined as the date the decision was made to end IP as recorded on the End of Investigational Product Administration CRF page.

End of Study (Individual Subject):

End of study for each subject is defined as the date the subject last completed a protocol-specified procedure. The date will be recorded on the End of Study CRF page.

End of Study (Primary Completion):

It is defined as when the last subject is assessed or receives an intervention for the purposes of final collection of data for the primary endpoint(s), whether the study was conducted as planned in the protocol or was terminated early.

End of Study (End of Trial):

The end of study date is defined as the date when the last subject across all sites is assessed or receives an intervention for evaluation in the study (ie, last subject last visit), following any additional parts in the study (eg, long-term follow-up), as applicable.

Fridericia-corrected QT Interval (QTcF):

The Fridericia correction will be calculated from the investigator reported QT (msec) and RR interval (msec), as follows:

$$QTcF=QT/(RR/1000)^{1/3}$$

Investigational Product:

The term 'investigational product' is used in reference to AMG 510.

[REDACTED]

Last Investigational Product Dose Date:

The last IP date for each subject is defined as the latest date IP administered.

Long Term Follow-Up:

Following the SFU visit, there will be a LTFU period during which data will be collected on the subjects' health condition, disease status, survival and subsequent anticancer treatment.

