9.6.2 Adverse Events

The Medical Dictionary for Regulatory Activities (MedDRA) version 21.0 or later will be used to code all events categorized as adverse events to a system organ class and a preferred term.

The subject incidence of adverse events will be summarized for all treatment-emergent adverse events, serious adverse events, adverse events leading to withdrawal of investigational product, and death due to adverse events.

Subject incidence of all treatment-emergent adverse events, serious adverse events, adverse events leading to withdrawal of investigational product, and fatal adverse events will be tabulated by system organ class and preferred term in alphabetical order.

The number and percentage of subjects reporting adverse events will be evaluated overall and by dose level and will also be tabulated by relationship to study drug.

The severity of each adverse event will be graded using The Common Terminology Criteria for Adverse Events (CTCAE) version 5.0 criteria.

- <http://ctep.cancer.gov/protocolDevelopment/electronicapplications/ctc.htm>.

Summaries of treatment-emergent and serious adverse events will be tabulated by system organ class, preferred term, and grade.

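### The SAP's treatment-emergent window can close at a subject's last completed procedure, so a collected event that starts later, within 30 days of the last dose, is left out of treatment-emergent and treatment-related incidence

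*Supplement*

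**What the plan says.** The current SAP (Amendment 1, v2.0), section 5, Treatment-Emergent Adverse Event, opens the window at first dose and closes it "up to and including 30 days after the last dose of investigational product or the End of Study date, whichever is earlier".

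Section 5 defines End of Study at more than one level:

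- For the individual subject: "End of study for each subject is defined as the date the subject last completed a protocol-specified procedure". This date is recorded on its own CRF page.
- For the trial: "The end of study date is defined as the date when the last subject across all sites is assessed".

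The TEAE entry does not say which is meant. The same section makes a treatment-related AE a subset of the treatment-emergent ones.

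The protocol (Amendment 3) sets the collection periods separately. Section 9.2.1.2 requires reporting of serious events "that occur after signing of the informed consent through 30 days after the last day of the dosing interval of investigational product". Section 9.2.1.1 covers non-serious events "that occur after enrollment through the safety follow-up visit are reported using the Event CRF". Section 7.2.3 says "the EOT visit should occur as soon as possible (within 14 days) after the last dose of investigational product". Section 7.2.4 places the safety follow-up visit about 30 (+7) days after the last dose, or before any new anticancer treatment.

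**The concern.** The collection window for serious events and the analysis window do not match. The protocol gathers serious events for 30 days after dosing ends. The SAP then discards any that start after the subject's last procedure, if End of Study is read at subject level.

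The discarding is informative. A subject who stays well attends the safety follow-up visit and keeps the whole window. A subject who deteriorates and dies shortly after stopping drug has no later procedure, so the window closes early. The events removed are those that prevented the next visit.

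Incidence of treatment-emergent and treatment-related AEs is a phase 1 primary endpoint (protocol 10.1.1.1.1.1; SAP 2.1.1). Incidence and severity of AEs is a secondary endpoint in phase 2. An event cut from the treatment-emergent set is lost from the treatment-related set as well.

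**Working it through.** The plan gives no figure to reproduce. The check applies the written rule to dates.

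**Notation.** D = day of last dose. E = End of Study day, read at subject level as the day of the last completed protocol procedure. Window end W = min(D + 30, E). Days of the 30-day window lost = max(0, D + 30 − E).

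**Which definition of E applies.** Three things favour the subject-level date:

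- The TEAE rule is applied subject by subject, and the individual date is a CRF field.
- The protocol's serious event form instructions (Appendix B) use the same term for the individual: "If the subject has already completed the study or terminated the study early, enter the End of Study date".
- At trial level, the cap could act only on subjects dosed within 30 days of the last subject's last visit, so it would do almost nothing.

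**Cases on the subject-level reading**

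| Last completed procedure | E | Days lost |
|---|---|---|
| Safety follow-up visit, on schedule | D + 30 to D + 37 | 0 |
| A long-term follow-up contact after day D + 30 (if it counts as a procedure) | later than D + 30 | 0 |
| End-of-treatment visit | D to D + 14 | 30 − 0 = 30, down to 30 − 14 = 16 |
| Last dose itself (if dosing counts as a procedure) | D | 30 |
| A clinic visit before the last dose (only if home dosing and diary entries do not count) | before D | the whole 30 days, plus some days on drug |

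**Worked example (dates assumed for illustration).** The last dose is day 60. The end-of-treatment visit on day 64 is the last procedure. A fatal event starts on day 70, and there is no safety follow-up visit.

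- As written: W = min(60 + 30, 64) = min(90, 64) = 64. Since 70 > 64, the event is not treatment-emergent. Days lost: 90 − 64 = 26.
- Without the End of Study limb: W = 90. Since 70 ≤ 90, the event is treatment-emergent.
- For collection: day 70 is 10 days after the last dose, inside the period for serious events in protocol 9.2.1.2.

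**Limits.** The rule works on onset. An event that starts on or before the last procedure and later proves fatal is still counted. Where the subject has no End of Study date yet, the cap does not act.

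**The case against.** **The term could be trial-level.** The SAP entry that literally defines an end of study date is the trial-level one, and on that reading the clause is almost inert. This stands as far as it goes: the SAP is ambiguous. But a clause is then either an undefined cap or one that does nothing, and neither is a reason to keep it.

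**On-treatment events are probably safe.** From cycle 3 the scheduled phase 2 visits fall only on day 1 of each 21-day cycle. A reader might infer that most fatal events starting between visits are cut even while the subject is on drug. The documents do not support that. Protocol 7.2 takes the study procedures from the Schedule of Assessments. Tables 5 and 6 list dosing and patient diaries there as continuous through treatment, and section 7.2.2 has phase 2 subjects use the eDiary every day. If these count as procedures, E is at or near the last dose, and the loss is confined to events starting after both the last dose and the last procedure. The SAP does not settle the point, but this is the better-supported reading.

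**The fatal and serious tables may be unaffected.** A reader might also infer that reported fatal and serious event rates are biased downward. SAP 9.6.2 says "fatal adverse events will be tabulated by system organ class and preferred term in alphabetical order", listing fatal and serious events beside the treatment-emergent ones without clearly restricting them to that set. Protocol 10.5.3.2 is similar. An excluded event may still appear in those tables. What is clearly exposed is treatment-emergent and treatment-related incidence.

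**Many subjects lose nothing.** Subjects seen at day 30 or later keep the full window. For those lost to follow-up, later events are mostly unobserved anyway. For withdrawals of consent, the cap matters only for events reported between the last procedure and the withdrawal.

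**Little depends formally on these counts.** The study is single-arm and safety is summarised descriptively. The phase 2 primary endpoint is ORR, DLTs have their own 21-day window, and the phase 2 safety reviews have no formal stopping guideline. All of this limits the consequence without justifying the rule.

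**Conclusion.** The concern holds in a narrow form. On the subject-level reading, the SAP excludes from treatment-emergent and treatment-related incidence an event that starts within 30 days of the last dose but after the subject's last procedure. This will arise mainly with death or withdrawal between the last dose or end-of-treatment visit and the safety follow-up visit. The direction is downward, and the loss is concentrated in severe early events.

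The size cannot be derived. The documents give no rate of such events and do not say whether dosing and diary entries are procedures. If they are, the effect is probably small. The conclusion rests on one assumption, that End of Study is meant at subject level. Fatal and serious event tables cannot be said to be biased on this text. This is an inexpensive correction to a stated rule, not a threat to the trial's main conclusions.

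**What to change.** In SAP section 5, strike the End of Study limb, so that a TEAE is any event starting on or after first dose and no later than 30 days after the last dose. This agrees with the serious event collection period in protocol 9.2.1.2.

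If the sponsor wants to keep a subject-level cap, name it as such and define it as the latest of last procedure, last contact and death.

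The cost is one line of SAP text and one change to the event-flag derivation, made before database lock. The serious events concerned are already collected, so no new data are needed.
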